7.7 Analysis sets

7.7.1 *Intent to treat analysis set (ITT)*

The ITT analysis set will consist of all subjects randomized. In accordance with the ITT principle, all subjects randomized will be kept in their originally assigned treatment group.

7.7.2 *Modified intent to treat analysis set (mITT)*

The mITT set will consist of all subjects in the ITT set who completed at least one study treatment, assigned a treatment group as treated.

7.7.3 *Per protocol analysis set (PP)*

The Per-Protocol (PP) analysis set includes all patients from the mITT analysis set without any major protocol deviation who have evaluable data on at least one qualifying migraine attack.

7.7.4 *Statistical analysis of analysis sets*

The ITT analysis set will serve as the main set for safety assessments and the mITT set for all performance assessments.

The primary performance assessment will also be performed on the PP analysis set as a sensitivity analysis.

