Study Procedures	
Following successful screening, enrollment interview and signing of informed consent, participants will be provided with an active Nerivio Migra or identically looking sham device and trained to perform treatment and provide feedback via the smartphone application.
 
Baseline information including mean frequency and severity of migraine attacks, occurrence of other headaches, presence of ICHD-3 diagnostic criteria for migraine with and without aura and use of preventive and rescue medications will be recorded.
 
During roll-in stage, migraine status will be recorded and participants will be requested to complete a quality of life questionnaire.
 
Participants who successfully completed the roll-in stage will continue to the stage involving treatment of four qualifying migraine attacks. A qualifying migraine attack shall be preceded by at least 48 hours of freedom from headache. Participants will be instructed to activate the device at the onset of a qualifying migraine attack and manually adjust stimulation intensity to a level within the pre-defined range where it is perceivable but not painful. Patients will be requested to refrain from use of rescue medications prior to and during the first two hours after treatment with the device, and if they can not comply with this, record their use of medications in the smartphone application. Via the application, each participant will be asked to rate his/her migraine pain level using Pain Grades Scale with values 0-3 (no pain, mild, moderate, severe): (1) upon starting the treatment, (2) two hours after starting treatment, (3) 48 hours after start of the first treatment corresponding to current migraine attack. Participants will be also asked to provide feedback using the application regarding the time elapsed from start of migraine attack to start of the treatment. In addition, participants will be reporting their use of rescue medication and presence of nausea, photophobia, phonophobia and allodynia, as well as additional migraine symptoms.
 
In case of failure to provide feedback regarding pain level post-treatment, queries will be generated via EDC system and telephone follow-up will be performed by study investigator staff to solicit such feedback. After providing feedback at two hours post start of treatment and in case of pain recurrence, participants will be allowed to re-treat the attack using Migra device.
 
Adverse events will be reported.
 
Post study questionnaire will include patient global impression of change, blinding and usability assessments.

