The total number of patients to be treated in this study is up to 248 eligible patients (see section 7.5).

6.5.5 *Expected Study Duration for Each Subject*

Study duration per patient is 4 complete treatment cycles and no longer than 3 months from enrollment (whichever is fulfilled sooner).

6.5.6 *Point of Enrollment*

Patients are formally enrolled in the study once they are found eligible by inclusion and exclusion criteria, have signed an informed consent and received training on the use of the device. If the patient was not treated with the investigational device, the patient will be excluded from the mITT data analysis set.

6.5.7 *Patient Withdrawal Criteria*

Patients may be withdrawn from the study by the PI or sponsor, if any one or more of the following events occur:

- The patient wishes to withdraw from the study without providing any explanation.
- Patient is lost to follow-up.
- Refusal of the patient to continue treatment and/or follow-up observations.
- Serious adverse event.
- Significant protocol deviation/violation or noncompliance, either on the part of the patient or investigator.
- Decision made by the investigator that termination is in the patient's best medical interest.
- Device failure.
- Other ethical or clinical considerations upon investigator discretion.

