6.6.2 Visit and assessment schedule

The study requires two hospital visits: (1) for screening and device training and (2) end of study visit when the device is returned and end of study assessment is performed.

Screening and enrollment visit

During the screening visit, the following procedures will be performed:

- Review Inclusion /exclusion criteria and evaluate eligibility
- Informed consent signing
- Demographics and medical history review.
- History of migraines.

- Medication history and concomitant medication(s) review.
- Enrollment and randomization.
- Patients will receive the Narivio device and smart phone (per need)
- Patients will receive training on device and application operation and schedule of reporting.
- Completion of a questionnaire.
- Urine pregnancy test

End of study visit (3 months after enrollment)

During the screening visit, the following procedures will be performed:

- Participants will be asked about changes in concomitant medications and adverse events that have occurred during the study. Devices and smartphones will be returned.
- Completion of a questionnaire

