7.4 Sample Size Estimation

The sample size for this study was calculated to test the above described null hypothesis with a chi-squared test, even though the final analysis may employ a regression model.

In the pilot study, the percentage of responders in the relevant treatment arm was 30%, while the percentage of responders in the sham group was 6%. The latter result is consistent with sham response rates referenced in IHS Guidelines for Migraine Trials. Sample size calculations are based on a more conservative estimate of the sham group response rate of 10%, then a sample size to detect a difference between treated and sham groups (of 20%) with 80% power at a 5% level of significance will result in a total of 124 evaluable subjects, with 62 subjects randomized to the treated arm and 62 to the sham arm. Allowing for a ~10% drop-out rate, a total of 136 (68 treated vs. 68 sham) subjects may be enrolled in the study.

Statistical considerations require availability of 124 evaluable subjects, i.e. with data available for analyses. The study recruitment will be monitored closely via the EDC system and, as soon as the evaluable data target is achieved, the Study Monitor will receive notification. If the number of subjects enrolled in the US is at least 50% of the accumulated population, recruitment will be stopped.

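### The primary comparison groups subjects by device received, the as-randomised set is named only for safety, and a Mantel-Haenszel test is given an interaction purpose it cannot serve

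*Combined protocol and SAP*

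**What the plan says.** All references are to the combined protocol and SAP.

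- **ITT (7.7.1)** is everyone randomised; "all subjects randomized will be kept in their originally assigned treatment group".
- **mITT (7.7.2)** is the part of ITT "who completed at least one study treatment, assigned a treatment group as treated".
- **PP (7.7.3)**: this "analysis set includes all patients from the mITT analysis set without any major protocol deviation". It has no arm rule of its own.
- **Use (7.7.4)**: "The ITT analysis set will serve as the main set for safety assessments and the mITT set for all performance assessments". PP is the only other set named for the primary endpoint.
- **Never-treated subjects (6.5.6)**: "If the patient was not treated with the investigational device, the patient will be excluded from the mITT data analysis set".
- **Timing**: the screening visit in 6.6.2 includes "Enrollment and randomization". The one-month roll-in comes afterwards, and the Synopsis says "Participants who successfully completed the roll-in stage will continue to the stage involving treatment of four qualifying migraine attacks".
- **Missing data (7.8.7)** plans a worst-case analysis with missing counted as non-response, without naming a set.
- **Centers**: 7.8.5 gives a center-stratified Mantel-Haenszel test the task of assessing interaction between center and group. Section 7.9 plans a treatment-by-center term in a logistic regression for the same question, and 7.8.2.1 sets a 10% level for interaction.

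**The concern.** The grouping rules are the wrong way round. A randomised comparison of performance should follow the assigned arm; adverse events should be attributed to the device the subject wore. As written, a wrongly dispensed subject changes arm in the primary test, while that subject's adverse events stay under a device that was never used. PP does not repair this. It is drawn from mITT, and such a subject may also leave PP if the error counts as a major deviation under 10.1.

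The second issue is completeness. Anyone lost in roll-in, or who never completes a treatment in Stage Two, is randomised but outside mITT and therefore outside PP. The 7.8.7 analysis names no set, and since 7.7.4 assigns all performance work to mITT, it would not bring these subjects back.

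The third is the Mantel-Haenszel test. It tests a common treatment effect across centers, not whether the effect differs between them. Read as an interaction test, it can miss opposite effects, or be significant when every center shows the same effect. Poolability could then be judged on the wrong p-value.

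**Working it through.** **Inputs.** From 7.4: 30% v 10%, 62 evaluable per arm, two-sided 5%, and "Allowing for a ~10% drop-out rate, a total of 136 (68 treated vs. 68 sham) subjects may be enrolled in the study". From 7.8.5: an unstratified chi-squared test. All p-values below are Pearson chi-squared without continuity correction.

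**The plan's own figure.** With pooled variance, n per arm = [1.960·√(2×0.2×0.8) + 0.842·√(0.3×0.7 + 0.1×0.9)]² / 0.2² = 61.6, so 62 per arm and 124 in total. The stated size reproduces, with power 80.3% at 62 per arm.

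**Wrongly dispensed devices.** For a active and b sham responders out of n₁ and n₂, with N = n₁ + n₂, X² = N[a(n₂−b) − b(n₁−a)]² / [n₁n₂(a+b)(N−a−b)]. For 15/62 v 6/62, X² = 124×(15×56 − 6×47)² / (62×62×21×103) = 4.64, p=0.031. If one active-arm responder received a sham device, as-treated grouping gives 14/61 v 7/63: 124×(14×56 − 7×47)² / (61×63×21×103) = 3.09, p=0.079.

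| As randomised | Error | As treated | p before → after |
|---|---|---|---|
| 15/62 v 6/62 | active-arm responder given sham | 14/61 v 7/63 | 0.031 → 0.079 |
| 15/62 v 6/62 | active-arm non-responder given sham | 15/61 v 6/63 | 0.031 → 0.025 |
| 15/62 v 6/62 | sham-arm non-responder given active | 15/63 v 6/61 | 0.031 → 0.038 |
| 13/62 v 6/62 | sham-arm responder given active | 14/63 v 5/61 | 0.081 → 0.030 |
| 13/62 v 6/62 | active-arm non-responder given sham | 13/61 v 6/63 | 0.081 → 0.069 |
| 13/62 v 6/62 | sham-arm non-responder given active | 13/63 v 6/61 | 0.081 → 0.095 |
| 19/62 v 6/62 (planned effect) | three active-arm responders given sham | 16/59 v 9/65 | 0.004 → 0.066 |

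At the planned effect, one or two such errors leave p at 0.011 and 0.028.

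**Never-treated subjects.** Assumption: all 136 − 124 = 12 subjects allowed for drop-out never treat, and they count as non-responders in ITT.

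| Loss, active / sham | mITT | Full ITT | p mITT → ITT |
|---|---|---|---|
| 6 / 6 | 15/62 v 6/62 | 15/68 v 6/68 | 0.031 → 0.033 |
| 10 / 2 | 14/58 v 6/66 | 14/68 v 6/68 | 0.023 → 0.053 |
| 2 / 10 | 15/66 v 6/58 | 15/68 v 6/68 | 0.067 → 0.033 |
| 10 / 2, planned effect | 19/58 v 6/66 | 19/68 v 6/68 | 0.001 → 0.004 |

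A simulation of error rates points the same way. With 68 per arm, a true 10% response in both arms of the full randomised set, and all never-treated subjects non-responders, excluding 15% of active and 5% of sham subjects raises the chance of a false win for active from the nominal 2.5% to 4.1%. Excluding 5% of each leaves it at 2.5%.

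**Mantel-Haenszel.** The statistic sums observed minus expected active responders over centers before squaring, so opposite effects cancel. Take two centers with 31 per arm (an illustration).

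- Opposite effects, 12/31 v 3/31 and 3/31 v 11/31: the differences are 12 − 7.5 = +4.5 and 3 − 7 = −4, sum 0.5. The variances are 2.89 + 2.75 = 5.64. The statistic is 0.25/5.64 = 0.04, p=0.83. The Breslow-Day homogeneity test gives p=0.0003.
- Identical effects, 9/31 v 3/31 in both: the differences are 3 + 3 = 6 and the variances 2.46 + 2.46 = 4.92. The statistic is 36/4.92 = 7.3, p=0.007. Breslow-Day gives p=1.00.

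**The case against.** The case for leaving this alone has real content.

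- **Swaps should be rare and traceable.** Devices are numbered and issued in order (6.2.2), and the number is logged in the CRF and at the site (section 11). No error rate is given. A swap changes the conclusion only if it involves a responder, in the right direction, in a borderline result. All of this stands. But a log only lets an error be found; it does not decide which arm the subject counts in, and the present rule decides that wrongly.
- **Loss in roll-in has little reason to depend on arm.** Treatment mode is switched on only after Stage One, and subjects are blinded and have had only a training session. That stands for roll-in. It is weaker for Stage Two before a first completed treatment. The pilot's complete-reporting rates (4.2) of 70% for the three stronger programs and 28% for placebo show that behavior can differ by arm, although they count reports per activation, not subjects who never treat.
- **The 10 to 2 split is extreme.** If loss is unrelated to arm, a split of 12 at least that uneven has a two-sided chance of about 4%. It is a stress case, not a forecast.
- **Exclusions will be visible.** Section 7.8.4 requires reasons for discontinuation and a list of patients left out of the performance analysis. A list is not an analysis of everyone randomised.
- **7.7.4 calls ITT the main set for safety and does not forbid an ITT performance analysis.** True, but none is specified.
- **The Mantel-Haenszel point is a misstated purpose.** Section 7.9 already holds a valid interaction test, and success rests on the chi-squared test alone. Both stand; alone it would be an editorial note.

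**Conclusion.** The concern holds. These are stated rules that are wrong as written, not missing detail: performance follows the device received, safety follows the device assigned, no named performance analysis includes all randomised subjects, and one test is described as doing something it does not do.

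The effect on the result is conditional. The grouping rule matters only if a device is wrongly dispensed; then one responder can move a borderline result across 0.05 in either direction, while at the planned effect three adverse responder swaps are needed. Leaving out never-treated subjects matters only if loss differs between arms, and can then favor either arm. The sizes rest on assumed counts, because the documents give no rate for dispensing errors or for subjects who never treat. The Mantel-Haenszel wording does not touch the success rule. The change should be made because it is clear and cheap, not because a large bias has been shown.

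**What to change.** 1. In 7.7.2 and 7.7.3, group mITT and PP by randomised arm.
2. In 7.8.7, run the non-responder analysis on the full ITT set by randomised arm. As a sensitivity analysis it needs no change to the sample size. For scale, if 10% of each arm never treat, the rates become 0.9×30% = 27% and 0.9×10% = 9%, and power with 68 per arm is 78.6%.
3. In 7.7.4 and 7.8.6, report safety by device received among subjects exposed to a device. A line on whether the training session counts as exposure would help.
4. In 7.8.5, describe Mantel-Haenszel as a center-stratified test of the treatment effect, and refer interaction to the logistic term in 7.9 at the 10% level of 7.8.2.1. A pre-set rule for combining small centers is a useful but optional addition.

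The cost is wording in 7.7, 7.8.5 to 7.8.7 and, if centers are to be combined, 7.9. No new data, visits or patients are needed, because the device number is already recorded. It is best done before the unblinded interim look, so that the choice of set cannot follow the data.

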3.6 Principle of Operation

Once Migra is placed on the patient's arm (see Figure 3) at the onset of a migraine headache, the user turns the device ON and activates therapy via the Mobile Application.

Figure 3 - Nervio Migra ready for use

This target location is easily accessed independently by the patient without help and is discrete to maintain treatment privacy. The treatment delivered to the user is a weak electrical current to the skin via the electrodes.

The operation of Migra is controlled by mobile application software that was developed by the company. The application is installed and operated from the patient's smartphone device, and is used for the activation, termination and control (e.g. stimulation intensity control, status indications and more) of the device.

The communication between the Migra device and the Application software is performed wirelessly via standard Bluetooth protocol.

Duration of the stimulation program is pre-set to 25 minutes. At any point in time, however, the patient is able to stop treatment by one of three methods:

- Terminating the stimulation via the Mobile Application
- Turning off the device switch located on the outside of the armband
- Carefully removing the armband

Migra delivers a single, pre-set, active stimulation program, or a sham program. Programs characteristics are given in Appendix XX.

Device operation flow is presented in the figure below.

[figure not shown]

Figure 5. Device operation flow

At any moment in the course of treatment, user can stop treatment by terminating the stimulation via the smartphone application, or by turning off the switch on the wearable unit, or by simply removing the armband.

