6 DESIGN OF THIS CLINICAL STUDY

6.1 *Description*

This is a prospective, randomized, double-blind, sham controlled multi-center clinical trial “Migraine Treatment with Nerivio Migra electro stimulation device”. The study will enroll up to 248 patients diagnosed with migraine with and without aura, per the inclusion and exclusion criteria. These patients will be individually and randomly assigned to either treatment group or control group. For sham control, short electrical pulses of amplitude range similar to that of the treatment programs will be administered at very low frequency (0.1-0.5 Hz). The rationale underlying selection of sham control settings is that, on the one hand, pulses are perceivable and the user is able to manipulate their intensity similarly to the case of treatment programs, while, on the other hand, no clinically relevant treatment is delivered, based on existing knowledge of parameters range of electro stimulation treatments [5-7, 18].

Following successful screening, enrollment interview and signing of informed consent, participants will be provided with an active Nerivio Migra or identically looking sham device and trained to perform treatment and provide feedback via the smartphone application. Ratio between treatment and control groups will be 1:1.

Baseline information including mean frequency and severity of migraine attacks, occurrence of other headaches, presence of ICHD-3 diagnostic criteria for migraine with and without aura and use of preventive and rescue medications will be recorded.

Investigational devices will be programmed in active or sham mode with a 1:1 ratio, in order to achieve the desired ratio between active and control groups sizes, stratified with by use of preventive medications.

Study flow is schematically presented in the figure below.

[figure not shown]

Figure 4. Study Design

Following enrollment, the study will be conducted in three stages.

Stage One. In stage one (roll-in phase) recruited participants will be reporting their migraine attacks per ICHD-3 diagnostic criteria, including presence of aura, using an electronic migraine diary installed on their smartphones. Duration of this phase is one month.

Stage Two. This will be the parallel arm treatment stage.

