6.4.4 Data Flow and Management

Data management function will be supported by a cloud based EDC system developed by Clear Clinica (Modi'in, Israel). Clear Clinica provides services for collection and remote monitoring of clinical trials data, compliant with HIPAA and 21 CFR Part 11.

EDC portals with secure authorized access will be made available to every participating site, as well as to the study monitor.

Data captured by clinical personnel will be entered directly into pre-specified eCRF screens by site personnel. Data from paper sources will be entered into the study database. Automatic data checks will be implemented for majority of entry fields to provide opportunity for resolving data inconsistencies as close as possible to real time. Effort will be made to identify missing or incorrect data and resolve the issues promptly.

Data collected onto the smartphone application will be directed to a secure cloud based database where it will undergo analysis aimed at detection of missing data and other inconsistencies. The smart phone will transmit PRO and technical data containing activation times, stimulation intensity and ePRO via the smartphone to a central electronic database for analysis. Activities such as repeatedly aborted programs, missing feedbacks, inconsistent stimulation intensity adjustments, and similar, will be communicated to research coordinator of the corresponding site, using participants' ID codes. Automated means were developed to identify and provide corresponding notifications regarding events that may lead to protocol deviations and/or missing data, and which resolution may require involvement of study staff. Examples of such events include missing PRO data or low device battery level. An automated system was implemented to notify the participant, site study coordinator and Sponsor study monitor on the above events. Missing data will be identified automatically by a script running on Clear Clinica's cloud, and queries will be generated to participants and corresponding site study coordinator. Near real time detection of problems in accumulating data will allow timely generation and resolution of queries. Intermediate data processing and translation into eCRF format are performed at this stage. Processed data are further pushed into the EDC system.

Schematics of data flow are presented in **Figure 5**.

[figure not shown]

Figure 5. Schematics of data flow

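### The mITT set for the primary analysis requires a completed treatment (7.7.2), while 6.5.6 excludes the untreated; completed is undefined, and no named performance analysis restores subjects who start but never complete a session

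*Combined protocol and SAP*

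**What the plan says.** Section 7.7.2 admits to mITT those ITT subjects who "completed at least one study treatment". Section 7.7.4 assigns "the mITT set for all performance assessments", which includes the primary endpoint, and makes ITT the main set for safety. The only other set named for the primary endpoint is PP, which under 7.7.3 "includes all patients from the mITT analysis set without any major protocol deviation".

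Section 6.5.6 describes membership of the same set differently: "If the patient was not treated with the investigational device, the patient will be excluded from the mITT data analysis set".

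Section 3.6 presets the program to 25 minutes and adds: "At any moment in the course of treatment, user can stop treatment by terminating the stimulation via the smartphone application". Section 6.4.4 expects this to happen: "Activities such as repeatedly aborted programs, missing feedbacks, inconsistent stimulation intensity adjustments, and similar, will be communicated" to the site coordinator. Sections 6.1 and 6.4.2.2 time the 2-hour rating from the start of the program, not from its end.

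**The concern.** A subject who activates the device and stops every session early has been treated in the sense of 6.5.6 but, on the plain reading, has not completed a treatment in the sense of 7.7.2. Two programmers could build two different primary populations from the same protocol.

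Under 7.7.2, membership depends on behaviour after randomisation. That behaviour could differ by arm, because the stimulation differs: active runs at 100-120 Hz (Appendix A), whereas the sham pulses "will be administered at very low frequency (0.1-0.5 Hz"). If removal is unequal and related to outcome, the primary comparison is no longer between randomised groups. The choice of rule should not be left open until data have been seen unblinded.

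**Working it through.** **1. Does any named analysis bring these subjects back?**

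| Analysis | Set | Restores subjects who never complete a session? |
|---|---|---|
| Primary, secondary and exploratory performance (7.7.4) | mITT | No |
| Sensitivity analysis of the primary endpoint (7.7.3, 7.7.4) | PP, a subset of mITT | No |
| Worst case, missing = non-responder (7.8.7) | Not stated; mITT by 7.7.4 | No |
| Safety (7.7.4) | ITT | Yes, but not for performance |
| List of patients excluded from the performance analysis (7.8.4) | Listing | Shows them, does not analyse them |

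**2. What could completed mean?**

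- *The full 25-minute program.* Subjects who stop every session early are out, even with a 2-hour rating on file. One completed session keeps a subject in.
- *A treatment cycle with feedback.* Section 6.5.5 speaks of complete treatment cycles, so this is possible. Membership then depends on reporting. In the pilot (4.2), complete reporting was obtained for 70% of activations on the three stronger active programs, 58% on P50 and 28% on placebo.

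Either way the set is selected on something observed after randomisation.

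**3. The plan's own figure.** Section 7.4: 30% vs 10%, 80% power, two-sided 5%, 1:1, chi-squared test. Without continuity correction,

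n = [1.96·√(2·0.20·0.80) + 0.8416·√(0.30·0.70 + 0.10·0.90)]² / 0.20² = (1.1087 + 0.4610)² / 0.04 = 61.6,

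which rounds up to 62 per arm and 124 in total, as stated (power 80.3%). The point does not change this figure; it shows that the uncorrected test is the right one for step 4.

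**4. Illustration of size.** The documents give no stopping rates, so the counts below are assumptions. Take 62 treated subjects per arm and remove s of them, all non-responders. A true rate p among all treated then appears as p × 62/(62 − s); for p = 10% and s = 6 this is 0.10 × 62/56 = 11.1%. The probability that the uncorrected chi-squared test gives p < 0.05 with active ahead is found by exact binomial enumeration over all outcomes. The interim analysis and any replacement recruitment are ignored.

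True rate 10% in both arms:

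| Removed, active | Removed, sham | Rate seen, active | Rate seen, sham | False device win |
|---|---|---|---|---|
| 0 | 0 | 10.0% | 10.0% | 2.5% |
| 3 | 0 | 10.5% | 10.0% | 3.0% |
| 6 | 0 | 11.1% | 10.0% | 3.8% |
| 9 | 0 | 11.7% | 10.0% | 5.3% |
| 6 | 6 | 11.1% | 11.1% | 2.5% |
| 0 | 6 | 10.0% | 11.1% | 1.5% |

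True rates 20% vs 10%: the chance of success is 34% with nobody removed, 44% with 6 removed on active only, 35% with 6 removed in each arm, and 26% with 6 removed on sham only.

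For the planned active rate of 30% among all treated, removing 5% of the arm as non-responders gives 0.30/0.95 = 31.6%; removing 10% gives 0.30/0.90 = 33.3%.

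**5. Attack level.** The endpoint in 7.2.1 is a share of treated attacks, and the plan does not say whether an aborted session counts as one. A subject who aborts 2 of 4 sessions and is pain-free in 1 of the other 2 scores 1/4 (non-responder) if aborted sessions count and 1/2 (responder) if they do not.

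**The case against.** Several stronger readings are tempting, and the documents do not support them.

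- *That the bias favours the device.* A reader might infer that stopping for discomfort happens mainly on active. But sham pulses have a similar amplitude range (6.1), subjects set the intensity themselves to a non-painful level (6.1), and each must first run a training session independently (3.9). The pilot reported no device-related adverse events or side effects (4.2) and good tolerability (4.3.2). If completed means a cycle with feedback, and the pilot reporting pattern recurred, removals would fall mainly on sham and work against the device. The pilot percentages concern reporting per activation, not aborted sessions, so they settle nothing either way.
- *That the rule hides poor tolerability.* It does not. Safety uses ITT; tolerability and failure to complete the study are reported by group (7.8.6); discontinuation reasons and patients excluded from the performance analysis are listed (7.8.4).
- *That aborted sessions are dropped from treated attacks.* No passage says so. Section 7.7.2 selects subjects, not attacks. Step 5 shows a gap in the definition, not a stated rule.
- *That 6.5.6 flatly contradicts 7.7.2.* Section 6.5.6 says the untreated are excluded; it does not say that nobody else is. Both rules can be applied together. They still give different criteria for one set, and 6.5.6 mentions no other exclusion.

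It is also fair that exclusion requires every session to be incomplete, so the number affected may be small. What stands is that completed is undefined, the two sections differ, and no named performance analysis includes everyone who started treatment.

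**Conclusion.** The point holds as a defect in the definition of the primary population. Its effect cannot be sized from the documents. With 6 non-responders removed out of 62 per arm, the false-win chance ranges from 1.5% to 3.8% around the nominal 2.5%, depending on which arm loses them, and it is unchanged when both arms lose 6. These figures rest on assumed counts and on every removed subject being a non-responder. The plan should be corrected because the set is chosen after randomisation and the wording allows more than one primary population. Nothing in the documents shows that the trial is biased towards the device.

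**What to change.** - **7.7.2:** replace the completion criterion with: *started at least one Stage Two treatment (device activation in the application log, training sessions excluded), whatever its duration*. This agrees with 6.5.6. Training sessions already carry their own label in the study database (3.9).
- **7.2.1:** state that an attack counts as treated once stimulation is started, including sessions stopped early.
- **7.8.6:** add a table of sessions stopped before 25 minutes, by arm, from the activation and deactivation logs already kept (3.3, 6.4.1).

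Settle the wording before the unblinded interim at 62 evaluable subjects (7.5). The cost is two sentences and one table from data already captured, with no change to the planned 124. The downside is that the response rate may be slightly lower in either arm.
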